An adverse event (AE) is any untoward medical occurrence in a subject associated with the use of the therapy under the study whether or not related to Intellis™ SCS system or the study procedures. An AE is also any event related to any underlying medical condition, present at baseline, which increases in severity or frequency by a clinically meaningful amount during the study as determined by the Investigator.

For all adverse events, the Investigator will provide an assessment of the adverse event, its seriousness, treatment/intervention provided, relationship to the device/procedure, and resolution.

As the efficacy measures in this study are back and leg pain, back and leg pain do *not* need to be reported as an adverse event unless it meets the definition of a serious adverse event. Investigators may, however, report any other pain-related adverse events during the study.

Pre-existing conditions will not be reported as an adverse event unless there has been a substantial increase in the severity or frequency of the problem, which has not been attributed to its natural history.

A serious adverse event (SAE) is an adverse event that

- Leads to death
- Leads to serious deterioration in the health of the subject, that either results in
 - a life-threatening illness or injury (life-threatening is defined as at risk of death at the time of the event), or
 - a permanent impairment of a body structure or a body function, or
 - in-patient hospitalization or prolongation of existing hospitalization (in-patient hospitalization is defined as a hospital admission for a period of greater than 24 hours), or
 - medical or surgical intervention to prevent life-threatening illness or injury or permanent impairment to a body structure or a body function,
- Leads to fetal distress, fetal death, or a congenital abnormality or birth defect

Those known adverse events related to the device, procedure or therapy are listed in the section C. (Risk Analysis) of this Investigational Plan.

B.8.3.2 Reporting

All AEs and SAEs will be assessed and captured from enrollment through the completion of the study on the Adverse Event Case Report Form (AE-eCRF). AEs and SAEs will be reported as required by the IRB. However, as would be the common practice when using commercial medical devices, device -related AEs may be reported by the site (per their institutional policy) to the Customer Service or Technical Support of Medtronic as specified in the manufacturer's labeling/manuals.

All Adverse Events (see list in section C.1.) reported during the study will document seriousness, treatment/intervention provided, relationship to the device/procedure, and resolution.

[figure not shown]
This is a post market, open-label study so Data Monitoring Committee will not be used.

B.9. Data Collection and Analysis

B.9.1. Data Collection

Study data will be collected using a secure Electronic Data Capture system meeting the requirements of 21 CFR part 11. Each data field completed via the EDC system is expected to have a verifiable source document. The clinical site will enter directly the data on outcome variables as well as adverse events should they occur. Subject confidentiality will be maintained, and each subject will be identified only by the assigned study subject number. Subject names will not be published.

Data collection is summarized in Table 1.

B.9.2. Statistical Analysis

Descriptive statistics will be used to summarize baseline and outcome data collected during the study. Continuous variables will be summarized using means, standard deviations, and ranges. Categorical variables will be summarized in frequency distributions.

B.9.2.1 Primary Analyses

The *primary efficacy endpoint* will be evaluated with a Farrington-Manning binomial test for non-inferiority at the one-sided 0.05 alpha level.

H_0 : The percentage of subjects (P) who achieve a 50% improvement in their back VAS pain score at 3 months in the Test group is inferior to that in the Control group.

$$P_{\text{Test}} \leq P_{\text{Control}} - 10\%$$

H_1 : The percentage of subjects (P) who achieve a 50% improvement in their back VAS pain score at 3 months in the Test group is not inferior to that in the Control group.

$$P_{\text{Test}} > P_{\text{Control}} - 10\%$$

A 10% margin has been previously used in a similar study.⁸ Meeting the statistical threshold for this test based on a 10% margin should produce clinically acceptable results.

B.9.2.2 Secondary Analyses

The following *secondary endpoints* will be evaluated:

- If the primary efficacy endpoint in the test group is found to be non-inferior to that in the control group, then a secondary endpoint will evaluate whether the proportion of subjects who achieve a 50% improvement in their back pain VAS score at 3 months in the test group is superior to that in the control group. A superiority test based on the difference in proportions will be performed based on the following null hypothesis, with a one-sided p-value of 0.05 or less considered evidence of statistical significance.

H_0 : The proportion of subjects (P) who achieve a 50% improvement in their back pain VAS score at 3 months in the Test group is less than or equal to that in the Control group.

$$P_{\text{Test}} \leq P_{\text{Control}}$$

H_1 : The proportion of subjects (P) who achieve a 50% improvement in their back pain VAS score at 3 months in the Test group is greater than that in the Control group.

$$P_{\text{Test}} > P_{\text{Control}}$$

- Change in mean VAS will be evaluated with two-sample t-test of non-inferiority in means with a 0.65 cm margin at 3 months.

H_0 : The change (C) in subject's VAS pain intensity score relative to baseline at the Primary Efficacy Assessment in the Test group is inferior to that of subjects in the Control group (active control).

$$C_{\text{Test}} \geq C_{\text{Control}} - 0.65 \text{ cm}$$

H_1 : The change (C) in subject's VAS pain intensity score relative to baseline at the Primary Efficacy Assessment in the Test group is not inferior to that of subjects in the Control group (active control).

$$C_{\text{Test}} < C_{\text{Control}} - 0.65 \text{ cm}$$

The non-inferiority margin of 0.65 cm was selected based on a previous study of a similar therapy against traditional SCS.⁸ In that study, the experimental therapy showed a 4.9 point improvement while traditional SCS showed a 3.6 point improvement for a difference of 1.3 points. Taking 50% of this treatment effect yields the margin of 0.65.

The following secondary endpoints do not have an associated hypothesis, and no significance level will be assigned to statistical tests that may be performed.

- Comparison of Back Pain Treatment Success (responder rate), measured as subjects with at least a 50% reduction in Back Pain VAS, evaluated at 6-months after device activation, between test and control:
- Comparison of mean change from Baseline in Back Pain VAS, evaluated at 6-months after device activation, between test and control

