Approximately 250 subjects will be enrolled at up to 15 clinical sites in the United States in order to include an estimated 125 subjects to the point of randomization and trial phase. This would allow at least 100 subjects (approximately 50% in each treatment arm) to complete the 3-month endpoint. Sample size estimates are discussed further in section B.5.5 of this Investigational Plan.

B. Protocol

B.1. Rationale for Study

It is estimated that about 20% percent of the population worldwide is affected by moderate to severe chronic pain¹. Chronic pain becomes a burden to the individual as this affects a person's ability to carry out many daily life activities, such as exercising, walking, driving a car, attending social events, or performing household chores. In the United States, chronic pain is considered one of the most pervasive and intractable conditions affecting at least one third of the population at an estimated cost of five hundred billion dollars per year, when combining health-related expenditure and the cost-impact on loss of productivity and income².

Conventional medical management, including medication and physical therapy, is often not adequate for treating chronic pain. Medication therapy based on opioids may also lead to addiction. Extensive use of opioid medications in the United States has led to the declaration of an epidemic crisis³. Furthermore, surgical interventions have also failed to remediate severe cases of neuropathies and intractable back pain for many patients. Spinal cord stimulation (SCS) is a proven therapy that has been in use for about 50 years for various types of chronic pain. SCS is a reversible therapy that allows patients to evaluate the therapy for several days using an external neurostimulator (ENS) prior to receiving an implantable neurostimulator (INS) system^{4,5,6,7}.

Spinal Cord Stimulation (SCS) utilizes pulsed electric fields that are applied to the dorsal section of the spinal cord via electrode arrays, called leads, implanted in the epidural space.

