Due to the nature of the programs, it is not feasible to blind the subjects, implanting physicians or the clinical site personnel to the SGX-SCS programming and Standard programming SCS group assignments. Each SCS group will be programmed under the direction of physicians with support of clinical representatives of the Test and Control treatments, which may identify the type of treatment to study participants. Also, open communication about sensation of paresthesia and pain relief is important in adjusting program parameters to provide optimal pain relief for subjects. The assessments of device performance are done by the subjects and not by the site personnel so the lack of blinding of site personnel should not affect results as pain is the major assessment and subjects tend to describe pain truthfully since it affects their everyday life dramatically and not be influenced by knowledge of the device programming. Despite the inability to blind the study, past SCS studies indicate that there is no reason to believe that subjects and Investigators/clinical staff will be influenced one way or another by the knowledge that a particular SCS program has been used.

B.5.5. Sample Size

Primary Endpoint Assessment occurs at the follow up visit 3 months after Device Activation. Based on the primary endpoint requirement, the estimated sample size of this study is at least 100 total subjects (at least 50 subjects in the SGX-SCS group and at least 50 subjects in Standard SCS group) who have passed screening requirements, have been randomized, and have completed the primary endpoint assessment.

The clinical investigational plan requires a screening process for all subjects that provide written informed consent. These subjects will undergo screening to assess eligibility. Subjects may be excluded for various reasons during screening. Accordingly, in order to include an estimated 125 subjects to the point of randomization and trial phase, approximately 250 subjects may need to be consented and enrolled to account for exclusions prior to randomization.

B.5.5.1 Sample size rationale and statistical power

The sample size estimate to determine primary endpoint is based on the primary objective of demonstrating non-inferiority of the test group to the control group. Established methods were followed in determining the non-inferiority criteria and the related sample size estimate

- Test basis: Farrington-Manning binomial test for non-inferiority

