- Estimated responder rate of 70% in the test group and 50% in the control group
- Significance level, alpha, of 0.05 one-sided
- Statistical power = approximately 90% or greater
- Non-inferiority margin of 10%
- Randomization: 1:1

Based on these assumptions, a minimum of 50 randomized and trialed subjects per treatment group (100 total) are required.

B.5.5.2 Overall Sample Size and Enrollment

Based on the primary endpoint requirement, a minimum of 50 subjects per treatment group are required (100 total). To account for a combined estimated attrition of 20% for subjects that do not complete the Trial Phase, and subjects that exit study before the 3-month primary endpoint visit, a total of 125 subjects would need to be randomized.

To account for 50% attrition prior to randomization (including subject ineligibility after signing the informed consent and subject dropout), it is estimated that a total of up to 250 subjects would need to be enrolled in the study.

[REDACTED]

[figure not shown]
[REDACTED]

[REDACTED]

[REDACTED]

B.6. Enrollment, Assessments, Randomization, and Clinical Procedure

Enrollment of subjects will occur at the clinical sites after Institutional Review Board (IRB) approvals, and when written informed consent from subjects has been obtained. Prior to enrollment, Investigators and clinical site staff will approach subjects, who have been determined to be candidates for SCS therapy and talk about potential participation in the study. Following informed consent, the eligibility of subjects to participate in the study will be assessed according to inclusion and exclusion criteria outlined in this Investigational Plan. Various assessments including pain intensity, evaluation of medical history and records, and the Investigator's clinical judgment will be used in the selection process.

B.6.2. Consent/Enrollment

Written informed consent for participation in the study must be obtained from subjects before initiation of any study-related activities, including those that assess eligibility. Following informed consent, subjects will be assigned a unique subject identification number and will be considered to be enrolled in the study. Eligibility for advancing to the next stage of the study will be evaluated by the site Investigator based on the defined inclusion and exclusion criteria. Subjects will be assessed for pain intensity and disability.

B.6.3. Entry Criteria Evaluation (0-14 days from Enrollment)

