The eligibility of subjects who have consented participation will be assessed based on the inclusion and exclusion criteria. Study subjects must meet all of the study inclusion criteria and none of the study exclusion criteria to be eligible. Assessments for eligibility include average pain intensity (which will be used as Baseline pain intensity), medication usage, medical records and history, and the Investigator's clinical judgment. Subjects with confirmed eligibility will proceed to Baseline assessment, while subjects who do not will be discontinued from the study.

B.6.4. Baseline

Before a subject is randomized, a subject will be requested to fill out standard questionnaires that will assess extent of disability, use of medications, and quality of life. The medical and surgical history of the subject will be collected. At this visit and subsequent visits, the subject will be assessed for adverse events, medication usage and be reminded to not increase pain medications from baseline through the 3-Month Visit.

Pre-operative assessments will follow the standard of care for SCS therapy and be determined by the site Investigator.

B.6.5. Randomization

Subsequent to completing Baseline assessments, qualifying subjects will be randomly assigned to either one of the two study treatment groups: SGX-SCS programming or Standard SCS programming (active comparator). Randomization will be stratified by gender and whether the subject has bilateral or unilateral leg pain at Baseline. Randomization will be done at each study site by randomly permuted blocks.

B.6.6. SCS Trial Phase

Subjects will undergo a Trial Phase with the randomly assigned treatment group. The Trial Phase will last up to 10 days. Percutaneous leads will be placed in the epidural space at a

vertebral level based on the subject's pain condition and pain pattern as described in the Physician Implant Manual. Stimulation will be delivered from an external neurostimulator (ENS).

Anterior-posterior (AP) and lateral X-ray imaging will be done following lead implantation at the beginning of the Trial Phase and when significant lead migration is suspected.

Stimulation therapy will be as follows for each study arm:

- For Standard SCS: stimulation parameters will be trialed according to standard practice as described in the Intellis™ labeling/manuals.

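### The responder tests (B.9.2.1, B.9.2.2) ignore the two randomization strata: valid and if anything conservative, but a stratified test with a named variance correction would recover a little precision

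*Combined protocol and SAP*

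**What the plan says.** - **Randomization (B.6.5).** "Randomization will be stratified by gender and whether the subject has bilateral or unilateral leg pain at Baseline". The next sentence adds: "Randomization will be done at each study site by randomly permuted blocks". Block size is not given. The synopsis and A.3 allow up to 15 sites.
- **Primary test (B.9.2.1).** The endpoint "will be evaluated with a Farrington-Manning binomial test for non-inferiority at the one-sided 0.05 alpha level". The hypotheses concern the overall responder percentages with a 10-point margin. No stratum or covariate is named.
- **Responder superiority (B.9.2.2), tested only if non-inferiority is shown.** "A superiority test based on the difference in proportions will be performed", again with no strata.
- **Sample size (B.5.5.1).** The trial is sized on the same unstratified test. The planning rates are: "Estimated responder rate of 70% in the test group and 50% in the control group". The other inputs are a one-sided level of 0.05, a margin of 10% and power of about 90% or more, giving 50 per group. B.5.5.2 raises 100 to 125 randomized.
- **Missing data (B.9.2.4).** Failed trial phases carry their trial-phase result forward; other missing data are multiply imputed.

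Text after the secondary analyses and in B.9.2.4 is redacted and could hold a supportive adjusted analysis. B.9.2.1, which defines the primary test, is readable.

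**The concern.** Stratifying on two factors treats them as plausibly related to response. If they are, randomization removes part of the between-stratum variation from the comparison of arms, but the crude variance still counts it. The standard error is then somewhat too large, so the test runs a little under its nominal level and loses a little power. Any imbalance left on the factors also goes unadjusted.

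Study success is declared on this one test (B.8.2). Non-inferiority has power to spare at the planned rates. The gated superiority test has much less, so lost precision costs more there. Adding a stratified analysis after results are known would look like choosing by outcome, especially in an open-label trial, so the choice belongs in the plan now.

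**Working it through.** **1. The plan's own figure.** Inputs from B.5.5.1: 70% and 50%, margin 0.10, one-sided 0.05, power 90%. The distance from the null is 0.20 + 0.10 = 0.30. The Farrington-Manning restricted estimates under the null are 0.5441 (test) and 0.6441 (control).

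- Null variance: 0.5441×0.4559 + 0.6441×0.3559 = 0.477
- Alternative variance: 0.7×0.3 + 0.5×0.5 = 0.46
- n per arm = (1.645√0.477 + 1.282√0.46)² / 0.30² = 44.7, so 45
- Power at 50 per arm = Φ[(0.30√50 − 1.645√0.477)/√0.46] = Φ(1.452) = 92.7%; exact enumeration also gives 92.7%
- 100/(1 − 0.20) = 125 randomized

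The plan's 50 per group and 125 randomized reproduce.

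**2. What ignoring the strata costs, by formula.** Assumptions not in the documents: four equal strata; gender shifts the response rate by a and laterality by b in both arms; perfect balance. The between-stratum variance per arm is B = (a² + b²)/4, and stratifying removes 2B. At 70% versus 50% the variance falls from 0.46 to w = 0.46 − 2B. With 50 per arm and d = 0.30 (non-inferiority) or 0.20 (superiority), using unpooled variances:

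- crude power = Φ[(d√50 − 1.645√0.46)/√w]
- stratified power = Φ[d√50/√w − 1.645]
- crude size at the margin (control 50%, test 40%, variance 0.49) = P(Z > 1.645√(0.49/(0.49 − 2B)))

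| Shifts a/b (points) | w | Non-inferiority power, crude → stratified | Superiority power, crude → stratified | Crude size |
|---|---|---|---|---|
| 0/0 | 0.460 | 93.1% → 93.1% | 67.0% → 67.0% | 5.0% |
| 10/10 | 0.450 | 93.3% → 93.5% | 67.2% → 67.8% | 4.8% |
| 10/20 | 0.435 | 93.6% → 94.2% | 67.5% → 69.1% | 4.6% |
| 20/20 | 0.420 | 94.0% → 94.8% | 67.8% → 70.4% | 4.3% |
| 20/30 | 0.395 | 94.5% → 95.8% | 68.3% → 72.8% | 3.9% |

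For 10/10 to 20/20 shifts, the ratio w/0.46 is 0.98 to 0.91, worth 50×(1 − ratio) = about 1 to 4 subjects per arm.

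**3. Site blocks.** Perfect balance is the extreme case. Blocks within site and stratum give up to 15×4 = 60 cells, about 125/60 = 2 subjects each. Balance on the two factors is then incomplete, and the crude size moves back toward 5%. Simulated crude size (100 or 125 subjects, control rate 50% or 60%, blocks of 4 assumed, 30,000 runs, Monte Carlo error about 0.12 points):

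| Shifts | Blocks within 15 sites | Blocks within the four strata only |
|---|---|---|
| none | 4.8–5.3% | 4.9–5.0% |
| 10/10 | 4.7–4.9% | 4.5–4.7% |
| 20/20 | 4.5–4.6% | 4.1–4.3% |

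Further site-block simulations gave about 4.9–5.2% at moderate effects and 4.2–4.4% at 20/30.

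**4. Simulated power at 70% versus 50%.** Non-inferiority, 50 per arm, crude versus stratified with the small-sample correction, blocks within site: 92.6% vs 92.7% (10/10) and 93.0% vs 94.1% (20/20). Superiority, 100 subjects, 8,000 runs, site or central blocks: 66% vs 67–68% (10/20), 65–66% vs 69% (20/20), 66–67% vs 71–72% (20/30), and 65.3% vs 65.2% with no prognostic effect.

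**5. The correction matters.** The stratified test without a small-sample correction ran at about 5.0–5.8%. With the Miettinen-Nurminen n/(n−1) correction it ran at about 4.7–5.4%.

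**The case against.** The best defence is that nothing is broken. An unstratified test after stratified randomization is valid, and B.9.2.1 uses the same test that sized the trial. Ignoring the strata does not make a false claim of non-inferiority more likely. Primary power is already about 93% at 50 per arm, and the documents report no effect of gender or laterality on response. All of this stands, and it limits the point to efficiency and consistency between design and analysis.

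Three stronger readings are tempting and not supported.

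- **That the primary test's true error rate is below 5%.** This needs prognostic factors, and a clear drop needs strong ones or blocks run only within the four strata; B.6.5 places the blocks at each site. Discreteness alone moves the exact size as much: 4.7% at 50 per arm and 5.8% at 62 per arm, with a control rate of 50%.
- **That about 3 points of primary power are being lost.** A simulation of 125 subjects does show 80.6% rising to 83.5%, but at a true difference of 12 points with shifts of 20 and 30 points. The plan assumes a difference of 20 points, and nothing in it supports such shifts.
- **That any stratified version holds its level.** Without the small-sample correction it can run slightly above 5%, so part of an apparent gain would be inflated size.

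The defence is also right that multiple imputation makes the change more than a one-word edit.

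**Conclusion.** The mismatch is real and stands in readable text: two stratification factors in B.6.5 and none in either responder test. It is a small efficiency and consistency point, not a validity failure.

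Under assumed shifts of 10 to 20 points, stratifying gains about 0 to 1 point of primary power at 70% versus 50%, and about 0 to 3 points of superiority power with 100 subjects. At 20 and 30 points the gains reach about 2, and about 4 to 6. With site-level blocks the crude size is close to 5% unless the factors are strongly prognostic. If they are not prognostic, crude and stratified power agree within simulation error.

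The direction is secure. The size rests on assumed prognostic effects, stratum shares, number of sites and block size. The change is still worth making, mainly for the superiority test, because it needs no subjects or data.

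**What to change.** - **Primary test (B.9.2.1).** Specify the stratified Miettinen-Nurminen score test of the Mantel-Haenszel-weighted risk difference over the four gender-by-laterality strata. Keep the 10% margin and one-sided 0.05. Name the n/(n−1) variance correction explicitly.
- **Site.** Leave it out of the strata; up to 60 cells for 125 subjects are too sparse.
- **Superiority test (B.9.2.2).** Use the same weighted risk difference.
- **Sparse strata.** Fix a pooling rule in advance, based on the number of subjects per arm rather than on outcomes, and apply it identically in every imputed data set.
- **Multiple imputation (B.9.2.4).** State how the stratified result is combined across imputations.
- **Sensitivity analysis.** Keep the crude Farrington-Manning test in this role.
- **Sample size.** Leave as stated; the crude test is the conservative basis.

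The cost is a few sentences of analysis text and slightly more programming, chiefly for combining imputations. No further data are needed.

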Stimgenics reserves the right to stop the enrollment of subjects at any clinical site at any time after the clinical site initiation. Possible reasons for suspending or terminating a clinical site may include, but are not limited to:

- Non-compliance by Investigator
- Failure to obtain proper written informed consent
- Repeated failure to complete or submit eCRFs in a timely manner
- Failure to report SAEs to the Sponsor within 48 hours of knowledge of the event and to reviewing IRB in accordance with its policies
- Repeated failure to comply with clearance of queries generated during monitoring of the study
- Inactivity

B.7. Study Endpoints

B.7.1. Definition of Analysis Populations

- Intent to Treat (ITT): All randomized subjects.
- Modified Intent to Treat (mITT): All randomized subjects who complete the Trial Phase.

B.7.2. Effectiveness Assessment Definitions

- Primary Effectiveness Assessment: For subjects who have a successful Trial Phase and receive a permanent implant, the Primary Efficacy Assessment occurs at the follow up visit 3 months after Device Activation. For subjects who do not have a successful Trial Phase, the Primary Efficacy Assessment occurs at the end of the Trial Phase.

B.7.3. Primary Endpoint

Pain rating on the 10 cm Visual Analog Scale is considered the primary outcome measure. VAS is the most widely used outcome measure in assessing pain due to its documented reliability and validity, ease in administration, and minimal training requirements for the administrator.

- ***Individual Responder:*** A decrease in back pain VAS by at least 50% at 3 months Post-Permanent Device Activation as compared with Baseline.

Overall Study Success: The percentage of Individual Responders in the test group is shown to be statistically non-inferior to the percentage in the control group.

B.7.4. Secondary Endpoints

The following secondary endpoints will be evaluated:

- Comparison of the percentage of Individual Responders between the test and control groups in a statistical test of superiority
- Comparison of change from Baseline in back pain score (VAS) determined at the 3-month visit after device activation, between test and control in a statistical test of non-inferiority. This is calculated as: Change from Baseline in Back Pain VAS = 3-Month Visit Pain VAS – Baseline Pain VAS. A negative result reflects a decrease in the Pain VAS, while a positive result reflects an increase in Pain VAS.

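### The 3-month mean back-pain VAS change has no pre-specified step from non-inferiority to superiority; adding one is cheap, but its power gain is likely rather than assured, and the printed VAS hypotheses must be reconciled first

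*Combined protocol and SAP*

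**What the plan says.** B.5.5.1 sizes the trial for one test: "Test basis: Farrington-Manning binomial test for non-inferiority", with "Estimated responder rate of 70% in the test group and 50% in the control group", "Significance level, alpha, of 0.05 one-sided", a 10-point margin and "Statistical power = approximately 90% or greater". This leads to 50 per arm, and B.5.5.2 raises the total to 125 randomized.

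B.7.4 lists as a secondary endpoint: "Comparison of the percentage of Individual Responders between the test and control groups in a statistical test of superiority". B.9.2.2 runs it only if the primary non-inferiority test succeeds, at one-sided 0.05: "A superiority test based on the difference in proportions will be performed based on the following null hypothesis".

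The same VAS is also analysed on its full scale: "Change in mean VAS will be evaluated with two-sample t-test of non-inferiority in means with a 0.65 cm margin at 3 months". No superiority step follows. The 6-month responder, 6-month VAS and 3-month ODI comparisons carry no hypothesis and no significance level. B.8.2 sets no success criterion for secondary endpoints.

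Some text is redacted or unreadable between B.7.4 and B.8.2, and between B.9.2.2 and B.9.2.4.

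**The concern.** The plan expects a true advantage. It assumes a 20-point difference in responders, and B.2 sets a secondary objective of showing further effectiveness against Standard SCS. Yet the one visible superiority question is put to a yes/no version of the VAS, which discards how far each subject lies from the 50% cut. The measurement that keeps this information is already a 3-month secondary endpoint, but its labelled test can conclude only that SGX-SCS is not worse by 0.65 cm.

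If the interval for the mean difference excluded zero, a superiority statement would be post hoc. Testing non-inferiority and then superiority on one interval costs no alpha within that endpoint, so a conclusion is given up that could be pre-specified for almost nothing.

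**Working it through.** **Inputs from the documents.** Responder rates 70% and 50%, margin 10 points, one-sided alpha 0.05, 50 per arm, 125 randomized (B.5.5.1, B.5.5.2); superiority at one-sided 0.05 and a cited mean VAS difference of 4.9 − 3.6 = 1.3 (B.9.2.2). **Not in the documents:** the SD of VAS change. It is taken as 2.0 to 3.5 cm.

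**1. The plan's own figure.** The unpooled approximation gives Φ(0.30/√(0.46/50) − 1.645) = Φ(1.483) = 93.1%. Farrington-Manning with restricted estimates gives 92.7%, asymptotically and by exact enumeration. The stated power reproduces, as does 100/0.80 = 125.

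**2. Responder superiority.** Power = Φ{[0.20 − 1.645·√(2·0.6·0.4/n)] / √(0.46/n)}.
- n = 50: (0.20 − 0.1612)/0.0959 = 0.405, so 65.7% (exact 65.8%).
- n = 62, all 125 randomized contributing fully: (0.20 − 0.1447)/0.0861 = 0.642, so 73.9% (exact 74.2%).

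**3. Full-scale superiority at zero difference, 50 per arm.**

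*Whole distribution shifts.* Moving responders from 50% to 70% on a normal scale is a shift of z(0.70) − z(0.50) = 0.524 SD. The noncentrality is 0.524·√(50/2) = 2.62, and t-test power is 83.1% (89.6% at 62). Simulations of change in cm used percent reduction that was normal with a ceiling, or beta, calibrated to 70%/50%. The assumed baseline had mean 7.3 and SD 1.2, limited to 5–10 cm. Power was about 77–78% after both non-inferiority gates, against 65–67% for responders.

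*Cited 1.3 cm difference.* The noncentrality is 1.3/(SD·√(2/50)) = 6.5/SD.

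| Assumed SD (cm) | 2.0 | 2.5 | 2.75 | 3.0 | 3.25 | 3.5 |
|---|---|---|---|---|---|---|
| Power | 94% | 83% | 76% | 69% | 63% | 58% |

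Break-even with the responder test is at SD = 6.5/(1.645 + 0.405) ≈ 3.2 cm.

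*Only the responder share differs.* Suppose relief among responders, and among non-responders, has the same distribution in both arms. With responders uniform on 50–100% and non-responders on −10–50%, power is 52%. With 60–100% and 0–40% it is 56%. Across such mixtures it is about 50–59%, below the responder test.

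**4. The printed VAS hypotheses.** B.7.4 defines a negative change as improvement. B.9.2.2 prints the alternative as C_Test < C_Control − 0.65 cm. Together these require the test arm to beat control by more than 0.65 cm, which contradicts the non-inferiority label. At a true 1.3 cm difference, the printed test has power 49%, 37% and 29% at SD 2.0, 2.5 and 3.0. With the margin on the non-inferiority side these become above 99%, 99% and 95%. Neither reading tests a zero difference.

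**5. Cost in false claims.** With the arms equal, simulation gives about a 5% chance of a false responder-superiority claim. Adding a gated VAS superiority test, not ordered against it, raises the chance of at least one false claim to about 7%; the rise is small because the two tests use the same VAS scores.

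**The case against.** Four objections carry weight.

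- **No promise is broken.** The design is sized for non-inferiority and meets that aim, and superiority is secondary. A reader might infer that 66% is a sizing error; the documents do not support that. The 66% also uses the minimum of 50 per arm, whereas ITT is all randomized subjects with multiple imputation, so power lies between 66% and 74%. This stands.
- **The gain depends on the model.** A reader might infer that the collected data would deliver about 80% power. No SD is given, and the ranking reverses if the arms differ only in who responds. The 40% Trial Phase threshold, with failures' results carried forward, makes such a split plausible. Against that, B.6.6 tunes therapy on graded self-reported relief, which fits a shift. Neither model can be excluded, so the gain is plausible but not assured.
- **Order of tests.** It is tempting to put VAS superiority ahead of responder superiority. The responder test follows directly from the primary endpoint, and the added step does not require moving it. If it were placed behind the VAS test with the printed inequality applied literally, its power would fall to about 17–28% in the shift models. This stands in full.
- **Redaction.** A full-scale superiority analysis could sit in unreadable text, so the point is limited to what can be read.

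None of this answers the remaining gap: no readable step takes the VAS interval to zero difference.

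**Conclusion.** The point holds as an optional improvement. The readable plan tests superiority only on the 50% cut, with 66% power at 50 per arm and at most 74%, given 70% v 50% and one-sided 0.05. It has no pre-specified route to superiority on the 3-month mean VAS change.

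The case for adding one is that it widens what the trial may conclude without new data. It does not rest on a guaranteed power advantage: the advantage is roughly 10–17 points under shift models, absent above an SD of about 3.2 cm for a 1.3 cm difference, and negative under the mixtures. The documents do not support reading this as a defect in the primary analysis, a power shortfall against a stated target, or a reason to demote the responder test. The conflict between the VAS label and its inequality is a separate textual fact that needs no assumption, and it must be settled before anything is gated on that test.

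**What to change.** 1. In B.9.2.2, reconcile the printed VAS hypotheses with the non-inferiority label, using the sign convention in B.7.4. At the same time settle which values Trial Phase failures contribute: B.7.4 computes change at the 3-month visit, while the B.9.2.2 hypotheses refer to the Primary Efficacy Assessment, which B.7.2 places at the end of the Trial Phase for failures.
2. Leave the primary test and the responder superiority test where they are. Add to B.7.4 and B.9.2.2:

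> If responder non-inferiority and then non-inferiority in 3-month mean back-pain VAS change are shown, superiority in 3-month mean back-pain VAS change will be tested one-sided at 0.05 using the same analysis set, Trial Phase-failure values and confidence interval.

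3. State that the two superiority tests are unordered, and disclose the rise from about 5% to about 7% in the chance of at least one false superiority claim when the arms are equal.

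The cost is a few lines of text, made before outcome data are seen, with no new subjects, visits or measurements.
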